# 2. Protocol Synopsis

Study to Evaluate Boston Scientific Vercise TM Cartesia TM 16-contact Directional Lead (X/HX) with Deep Brain Stimulation (DBS) Systems for the treatment of Parkinson's Disease (PD)				
	Cartesia eXTend 3D Study			
Study Objective(s)	To document patient outcomes including effectiveness for Boston Scientific Corporation's Vercise TM Cartesia TM 16-contact Directional Lead (X/HX) with Deep Brain Stimulation (DBS) Systems for the treatment of Parkinson's Disease (PD).			
Planned Indication(s) for Use	The Vercise Deep Brain Stimulation System is indicated for use in unilateral or bilateral stimulation of the subthalamic nucleus (STN) or internal globus pallidus (GPi) for treatment of levodopa-responsive Parkinson's disease which is not adequately controlled with medication.			
Test Device and sizes, if applicable	Boston Scientific's Vercise TM Cartesia TM X/HX 16-contact Directional Leads, 16-contact Lead Extensions and 16-contact Push Button OR Cable.  All other components of the DBS System are commercially approved.			
Study Design Prospective, multi-center, open-label confirmatory study with an adaptive design.				
Planned Number of Investigational Sites / Countries	Up to 15 global sites.			
Primary Effectiveness Endpoint	Mean change in MDS-UPDRS III scores from Baseline in meds off condition to 12 weeks post device-activation in stim on/meds off condition.			

Study to Evaluate Boston Scientific  $Vercise^{TM}$  Cartesia $^{TM}$  16-contact Directional Lead (X/HX) with Deep Brain Stimulation (DBS) Systems for the treatment of Parkinson's Disease (PD) Cartesia eXTend 3D Study Secondary Effectiveness **Endpoint** 

Study to Evaluate Boston Scientific VerciseTM CartesiaTM 16-contact Directional Lead (X/HX) with Deep Brain Stimulation (DBS) Systems for the treatment of Parkinson's Disease (PD) Cartesia eXTend 3D Study Screening Period (up to 45 days post informed consent) Study Visit Schedule Baseline Visit Implant procedures (up to 45 days post baseline visit) Device Activation (Day 0) Week 10 Visit post-activation (+ 7 days) Week 12 Visit post-activation (+ 7 days) Week 26 Visit post-activation (± 21 days) Years 1, 2, 3, 4 and 5 Visit post-activation ( $\pm$  45 days) Year 5 Visit will be the End of Study Visit.

## Cartesia eXTend 3D Study

Cartesia eXTend 3D Study

### Staged Procedures

Subjects may undergo staged surgical procedures prior to device activation, as determined by local standards of care

### Statistical Methods

[figure not shown]
### Primary Statistical Hypothesis

$$H_0: \mu_B - \mu_{12} \le 5$$

[figure not shown]
$$H_1 \colon \ \mu_B - \mu_{12} > 5$$

where  $\mu_B$  and  $\mu_{12}$  are the mean MDS-UPDRS III scores in *meds off* condition at Baseline and 12 weeks, respectively. The minimal clinically important difference (MCID) using MDS-UPDRS III scores (meds off) condition is assumed to be 5 based on Schrag et al. [24]

Cartesia eXTend 3D Study

		Page 17 of 74

Page 18 of 74

D	0 -	
Page 1	19 0	14

### 4. Introduction

### 4.1. Background

Parkinson's disease (PD) is a progressive neurodegenerative disorder that affects 5.2 million people worldwide [4]. The prevalence of PD is estimated at 0.3% of the overall population in industrialized countries and advances to 1% by age 60 and 4% in the highest age group [5]. The hallmark signs of PD include movement disorders such as bradykinesia, resting tremors, and muscle rigidity[6].

The motor symptoms of PD are associated with a dopamine deficiency resulting from the degradation of dopaminergic neurons in the substantia nigra pars compacta (SNc). At present there is no cure for PD; treatment is focused on medical management of motor symptoms. Medical therapy has been primarily focused on restoring dopamine levels through the administration of levodopa, dopamine agonists, or monoamine oxidase B inhibitors. Current standards for patient care recommend levodopa as first line of therapy for the symptomatic control during the early, uncomplicated stages of PD [7, 8]. Unfortunately, chronic treatment with levodopa frequently leads to significant side effects, especially dyskinesias and motor fluctuations [9].

Previously, for subjects who had reduced response to medical therapy, pallidotomy (destruction of the globus pallidus) and thalamotomy (destruction of the thalamus) were the only available treatment options. In the 1990s, high-frequency deep brain stimulation (DBS) was demonstrated to be effective in reducing the motor complications of subjects with PD [10]. Since that time, numerous case studies and trials have substantiated these early findings. In addition, six recent large, multicenter, randomized trials have demonstrated the effectiveness of the therapy [11-17].

Timmermann et al. published the results of Boston Scientific sponsored VANTAGE Study: a non-randomized, prospective, multicenter open-label study where 40 idiopathic PD patients at 6 European centers received bilateral STN DBS with VerciseTM DBS System [18]. The study successfully achieved its primary endpoint (p < 0.0001) and reported a mean difference of  $23.8 \pm 10.6$  points in MDS-UPDRS III scores in the stim ON/meds OFF condition at 6 months after implantation compared with Baseline.

Results from a large prospective, multi-center double blinded study with a sham control (INTREPID) using the Vercise™ DBS System reported a mean 6 hour improvement in ON time without troublesome dyskinesias (n = 160 randomized) at 1 year (PD diary) and

sustained improvement in motor function and quality of life measures thereafter up to 3 years [19].

Several systematic reviews and results from multi-center, randomized controlled trials provide solid evidence in support of the effectiveness and safety of DBS as a therapy for PD [17-19]. In addition, the review of published outcome studies has also shown that DBS is associated with favorable health economic and quality of life outcomes [20].

Recent advances in technology including directional stimulation has the potential to further improve patient outcomes. Several pilot studies have corroborated the use of directionality and its impact on therapeutic window and adverse effects [21-23].

This confirmatory study will document patient outcomes including effectiveness for Boston Scientific Corporation's VerciseTM CartesiaTM 16-contact Directional Lead (X/HX) with Deep Brain Stimulation (DBS) Systems for the treatment of Parkinson's Disease (PD). Additionally, safety parameters will also be collected.

## 5. Device Description

Boston Scientific DBS Systems are comprised of leads for stimulation and extensions that allow the leads to be extended to reach the Implantable Pulse Generator (IPG). The various components are shown in Error! Not a valid bookmark self-reference..

The Boston Scientific Vercise™ Cartesia™ X/HX 16-contact Directional Leads (30 cm or 45 cm) used with a commercially approved Vercise™ Genus 32-contact IPG will provide directional stimulation. These leads extend the span of contacts when compared with commercially available directional leads. However, the length of the distal contact array span is no greater than that of the existing standard DBS 8-contact Leads with non-directional arrays.

Once the leads are placed, they are typically secured using standard lead fixation technique. A commercially available SureTekTM Burr Hole Cover may be used. Since the leads are often placed under the scalp for some time before being connected to lead extensions or IPG, lead boots may be used to cover the proximal ends of the leads during this period. External commercially available devices, including a Clinician Programmer, Remote Control and Charging System, are provided for patient/physician use. Boston Scientific's GUIDE XT software may be used as a planning tool for programming as applicable.

The leads, lead extensions, and OR cable will be considered test devices in the study. All other components of the DBS system are commercially approved.

[figure not shown]

Figure 1: Cartesia X/HX 16-contact Directional Lead with Genus DBS System

### 6. Study Objectives and Endpoints

The primary objective of this confirmatory study is to document patient outcomes including effectiveness for Boston Scientific Corporation's VerciseTM CartesiaTM 16-contact Directional Lead(s) (X/HX) with Deep Brain Stimulation (DBS) systems for the treatment of Parkinson's Disease (PD). Additionally, safety parameters will also be collected.

### 6.1. Primary Endpoint

[figure not shown]
Mean change in MDS-UPDRS III scores from Baseline in *meds off* condition to 12 weeks post device-activation in *stim on/meds off* condition.

# 7. Study Design

The study is a prospective, multi-center, open label confirmatory study. The Cartesia eXTend 3D study meets all the requirements of a confirmatory study per ISO 14155 Annex I.

Subjects will receive the VerciseTM CartesiaTM (X/HX) 16-contact Directional Lead with the VerciseTM GenusTM DBS System and will be followed per study schedule as shown in Figure 2.2 below.

[figure not shown]

### 8.2. Inclusion Criteria

Subjects who meet all of the following criteria (see Table 8.2-1) may be given consideration for inclusion in this clinical investigation, provided no exclusion criterion (see Section 8.3) is met.

[figure not shown]
Table 8.2-1: Inclusion Criteria

### 8.3. Exclusion Criteria

Subjects who meet any one of the following criteria (Table 8.3-1) cannot be included in this study or will be excluded from this clinical study.

Table 8.3-1: Exclusion Criteria

# 9. Subject Accountability

#### 9.1. Point of Enrollment

A subject will be considered enrolled in this study at the time of the study-specific informed consent form (ICF) execution. No study-related procedures or assessments can take place until the ICF is signed.

#### 9.2. Withdrawal

All subjects enrolled in the clinical study (including those withdrawn from the clinical study) shall be accounted for and documented. If a subject withdraws from the clinical investigation, the reason(s) shall be reported. If such withdrawal is due to problems related to

investigational device safety or performance, the investigator shall ask for the subject's permission to follow his/her status/condition outside of the clinical study.

Reasons for withdrawal include but are not limited to:

- Loss of treatment efficacy
- Adverse events,
- physician discretion,
- subject choice to withdraw consent,
- subject's failure to meet the study's eligibility criteria after enrollment but prior to system implant,
- failure to receive the BSC DBS system,
- lost to follow-up,
- pregnancy\*,
- death,
- explant of the entire DBS system\*\*

While study withdrawal is discouraged, subjects may withdraw from the study at any time, with or without reason, and without prejudice to further treatment.

All applicable case report forms (CRFs) up to the point of subject withdrawal and an "End of Study" form must be completed. Any subject deemed "lost to follow-up" should have a minimum of three documented attempts to contact him/her prior to completion of the "End of Study" form.

Additional study data may no longer be collected after the point at which a subject has been withdrawn from the study or withdraws consent, for whatever reason. Data collected up to the point of subject withdrawal may be used. Subjects withdrawn after completing the implant procedure will not be replaced and will be included in the site's overall total for activated subjects.

- \*Women who become pregnant during the study, will be withdrawn and their device deactivated.
- \*\*If the entire DBS system of a study subject was explanted, it is recommended to follow the subject for 30 days after the explant of the system.

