#### 11.2. General Statistical Methods

#### 11.2.1. Analysis Sets

The following sets will be analyzed.

- Intent-to-Treat (ITT) Population: All subjects in which implantation of the device is attempted (successful or not), will be included in the ITT population. This will be the primary analysis set.
- Per Protocol (PP) Population: All subjects who receive the study device, with no major protocol deviations.
- Safety Population: All subjects who sign the IRB-approved written Informed Consent form

Subjects who have been withdrawn due to an explant or loss of treatment inefficacy will be analyzed as treatment withdrawals, while all other withdrawals will be considered as study withdrawals.

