# NOTES:

- Sensations or side effects that occur during programming should not be reported as AEs.
   However, persistent unpleasant sensations or side effects that occur after the completion of programming will be reported.
- Ineffective therapy (e.g. lack of efficacy, lack or decrease of therapeutic response) will not
  be collected as an adverse event, since failure to achieve therapeutic response is an issue of
  efficacy, not safety. No AE of "Ineffective Therapy" should be reported when using the
  expanded parameter range for purposes of improving ineffective therapy. However, AEs
  due to sudden loss of efficacy (e.g. loss of stimulation leading to a fall or injury) will be
  collected.
- The subject's Parkinson's disease symptoms will not be collected as AEs, unless they have
  worsened beyond baseline and beyond the expected disease progression over time. This
  worsening event could occur in the context of a device malfunction or with a properlyfunctioning device as determined by investigator).
- Device migration will not be collected as an adverse event. However, an AE that results from the device/lead migration should be reported as an AE. Device migration should be reported as a device deficiency in the electronic database.

In the case of death linked to device hardware or stimulation and/or procedure, autopsy and explantation of device is recommended. Every effort should be made to return the device to BSC. A copy of the death records including autopsy report should be sent to BSC per the Investigator Reporting Requirements (Table 19.4-1). The stimulator should be explanted in the case of cremation and returned to BSC. Cremation may cause the stimulator battery to explode.

Table 19.4-1: Investigator Reporting Requirements

Event Classification	Communication Method	Communication Timeline pre-market studies
		(21 CFR Part 812, /MDCG 2020-10/1)

For Germany, please also refer to the 'Serious Adverse Event Reporting according to MPKPV §3 (4) No. 7 & § 2 (1, 5) and §3 (4), (5), (7) & §5 (2) MPSV statement'.

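### Loss of efficacy is a reason for study withdrawal, and withdrawal ends data collection, so failing subjects have no later effectiveness score

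*Combined protocol and SAP*

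**What the plan says.** Section 9.2 (Withdrawal) gives an open list of reasons for withdrawal from the study, and the first entry is "Loss of treatment efficacy". It then states: "Additional study data may no longer be collected after the point at which a subject has been withdrawn from the study". Three further rules in that section bear on the point:

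- Reasons are recorded: "If a subject withdraws from the clinical investigation, the reason(s) shall be reported".
- Earlier data are kept: "Data collected up to the point of subject withdrawal may be used".
- Implanted subjects are not made up for: "Subjects withdrawn after completing the implant procedure will not be replaced".

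Section 11.2.1 (Analysis Sets) makes ITT the primary set and defines it as every subject in whom an implant is attempted. It says that subjects withdrawn for explant or for lost efficacy "will be analyzed as treatment withdrawals, while all other withdrawals will be considered as study withdrawals". That sentence speaks of loss of treatment *inefficacy*, apparently a slip for the term in 9.2.

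The primary endpoint (6.1, 11.1) is the change in MDS-UPDRS III from Baseline to Week 12, tested against a margin of 5 points (11.1.1). Sections 10.9 and 10.10 bring subjects back in the stimulation-on, medication-off state at Week 26 and at Years 1 to 5. Section 11.2.4 refers to the SAP for further analysis detail, and that detail is not in the text available.

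**The concern.** Section 9.2 uses one term, withdrawal, for two different things: the therapy no longer works, and the subject is no longer observed. Because the first is listed as a reason for the second, the outcome being measured can decide who is measured next. That is outcome-dependent missingness.

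ITT membership does not cure it. It settles who belongs in the denominator, not what score an unmeasured subject contributes. Being classed as a treatment withdrawal is a label, and no value follows from it in the text available. Keeping data up to withdrawal helps only for visits already attended, and nothing visible requires a last MDS-UPDRS III before the subject leaves.

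The study has a single open-label arm (Section 7), so no control group would reveal selective loss. If later visits are summarised as observed, the means increasingly describe subjects in whom the therapy still works. A missing-data rule in the SAP could model the absent scores but could not recover them. For that reason the point is first about data collection and only second about analysis.

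**Working it through.** The visible text gives no sample size, alpha, power or dropout rate for this study, so there is no figure of the plan to reproduce. The calculation below is an illustration.

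**Inputs**

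- m = 23.8 and SD = 10.6: mean change and SD in the earlier sponsor study (Section 4.1). They are not stated as planning values here. They are used for subjects who stay.
- Margin = 5 points (Section 11.1.1).
- f = share of implanted subjects who leave for lost efficacy before a given visit. Assumed, 2% to 20%.
- c = true mean change at that visit in those who leave. Assumed, 0 or 5 points.
- n = 20 or 40, and one-sided alpha 2.5% (critical z = 1.96). Assumed.

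**Bias of the as-observed mean**

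Mean for all implanted subjects = (1 − f) × m + f × c. The as-observed mean is m, so bias = f × (m − c).

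| f | Bias, c = 0 | All-implanted mean, c = 0 | Bias, c = 5 |
|---|---|---|---|
| 2% | 0.02 × 23.8 = 0.5 | 23.3 | 0.02 × 18.8 = 0.4 |
| 5% | 0.05 × 23.8 = 1.2 | 22.6 | 0.05 × 18.8 = 0.9 |
| 10% | 0.10 × 23.8 = 2.4 | 21.4 | 0.10 × 18.8 = 1.9 |
| 20% | 0.20 × 23.8 = 4.8 | 19.0 | 0.20 × 18.8 = 3.8 |

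With c = 0 the bias equals the 5-point margin at f = 5/23.8 = 21%.

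**Could it reverse the primary decision?**

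With c = 0 and the same within-group SD in both groups, the SD over all implanted subjects is √(10.6² + f(1 − f) × 23.8²). At f = 10% this is √(112.36 + 50.98) = 12.78. At n = 20, z = (21.42 − 5)/(12.78/√20) = 5.75, far above 1.96.

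- z falls below 1.96 only at f of about 50% (n = 20) or 58% (n = 40).
- The all-implanted mean falls to 5 only at f = 1 − 5/23.8 = 79%.

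If the effect is near that of the earlier study, the distortion is in the size of the estimate and not in the pass/fail result at Week 12.

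**The case against.** The strongest reply is that the plan does not lose sight of these subjects. They stay in ITT, have their own analysis class, have a reported reason and an End of Study form, keep their earlier scores and are not replaced. A subject who leaves after Week 12 still contributes the primary score. All of this stands, and it limits the point to scores after withdrawal.

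A second reply is that missing-data handling may be specified in text that is not available: the numbering passes from 11.2.2 to 11.2.4, and the SAP detail is not shown. This also stands. Upward bias is therefore conditional on an as-observed analysis, and absence of a rule cannot be claimed. The secondary endpoint and the assessment schedule are not visible either, so a later MDS-UPDRS III series is a reasonable assumption and not a stated fact. None of this supplies scores that 9.2 stops collecting.

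A third reply is that removing the entry from the list would achieve little. The list is open, does not oblige anyone to withdraw, and also contains physician discretion and subject choice, so the same subjects could leave under a less informative label. This is correct and shapes the fix.

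Two stronger readings are tempting.

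- A reader might infer that failures vanish from both the effectiveness and the safety data, because the notes to Section 19.4 say "Ineffective therapy (e.g. lack of efficacy, lack or decrease of therapeutic response) will not" be recorded as an adverse event. The documents do not support this. The same notes still collect adverse events from sudden loss of efficacy, and Parkinson's symptoms that worsen beyond baseline and expected progression. An adverse-event rule also cannot move an MDS-UPDRS III mean.
- A reader might infer that the primary test has an inflated false-positive rate. In simulation with a true mean of exactly 5, normal changes with SD 10.6, and the worst 5% or 10% removed before Week 12, the rate rises from 2.5% to about 6% or 12% (n = 20 enrolled) and 10% or 25% (n = 40). Those removed would have changes below 5 − 1.645 × 10.6 = −12.4 or 5 − 1.282 × 10.6 = −8.6, which is well worse than Baseline, and every one of them would have to leave within 12 weeks. Nothing in the documents makes that likely.

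**Conclusion.** The point holds in a limited form. Section 9.2 lets failure of the therapy end the measurement of its effect, and neither ITT membership nor the treatment-withdrawal class supplies the missing scores. If means are computed as observed, they are too high by f × (23.8 − c): about 1.2 points at 5% and 2.4 points at 10% with zero change in those who leave, or 0.9 and 1.9 points if they keep 5 points of benefit.

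These sizes rest on the earlier study's effect and on assumed withdrawal shares, for which the documents give no figure. The exposure lies mainly at Week 26 and Years 1 to 5. The Week 12 decision is unlikely to change if the effect is near 23.8 points. The point is worth acting on because scores not collected cannot be restored in analysis.

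**What to change.** **Protocol 9.2.** Separate loss of efficacy from withdrawal from study follow-up. Record the first as a treatment outcome with its date, and keep it as a reported reason so that 11.2.1 can still classify it. Subjects who still consent remain on the existing visit schedule and are scored in whatever stimulation state they are in. If a subject is leaving anyway and agrees, obtain the MDS-UPDRS III before the End of Study form is completed. This concerns data collection only and implies nothing about how the subject is treated.

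**Protocol 11.2.1.** Correct *inefficacy* so that the term matches 9.2, because the classification depends on it.

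**SAP.** State what value a treatment withdrawal takes in the mean change. Beside the observed-case mean, show a sensitivity analysis that gives unscored loss-of-efficacy subjects zero change. Zero is not a worst case, since a subject may be below Baseline, so this supports collection of the real score and does not replace it.

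**Cost.** A protocol amendment with ethics committee approval (Section 16.3), one further table, a few more medication-off ratings in subjects who are doing poorly (Section 18.4 lists discomfort during such testing as a risk of participation), and slightly less favourable later means.

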#### 9.3. Lost to Follow-Up

A subject is considered as lost to follow-up if they failed to return for scheduled visits upon several attempts of contact.

Before a subject is deemed lost to follow-up, the investigator or designee will make every effort to regain contact with the participant (where possible, 3 telephone calls and, if necessary, a certified letter to the participant's last known mailing address or local equivalent

methods). These contact attempts should be documented in the participant's medical record or study file.

Should the participant continue to be unreachable, he or she will be considered to have withdrawn from the study with a primary reason of lost to follow-up.

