#### 10.12. Study Completion

Subjects will be followed up to 5 years post-activation visit. Year 5 Visit will be considered their end of study and End of Study Action Plan will be followed as described in Section 9.7.

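### Sections 9.2 and 9.3 together bar all later data from an implanted subject who is declared lost to follow-up without having withdrawn consent, and give no route back

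*Combined protocol and SAP*

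**What the plan says.** Section 9.3 treats a subject as lost to follow-up who has "failed to return for scheduled visits upon several attempts of contact". Before that label is applied, the site must make every effort to regain contact: "where possible, 3 telephone calls and, if necessary, a certified letter to the participant's last known mailing address", or a local equivalent. If the subject still cannot be reached, "he or she will be considered to have withdrawn from the study with a primary reason of lost to follow-up".

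Section 9.2 lists loss to follow-up among the reasons for withdrawal and says that such a subject "should have a minimum of three documented attempts to contact him/her prior to completion of the" End of Study form. It then sets the consequence: "Additional study data may no longer be collected after the point at which a subject has been withdrawn from the study or withdraws consent". The sentence goes on to say that the reason does not matter. What was gathered earlier is kept: "Data collected up to the point of subject withdrawal may be used". Subjects withdrawn after implantation are not replaced. Permission for follow-up outside the study is sought only when withdrawal is due to problems with device safety or performance.

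On duration, Section 10.12 says "Subjects will be followed up to 5 years post-activation visit". Sections 10.9 and 10.10 place the later visits at Week 26 (± 21 days) and Years 1 to 5 (± 45 days).

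**The concern.** Loss of contact and withdrawal of consent are different events. A subject who withdraws consent has ended the permission to collect data. A subject who cannot be reached has not, and still carries the investigational lead. The protocol gives both the same consequence: the subject is closed and nothing further may be recorded.

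The two sections set no minimum time, number of missed visits or visit window before the status applies, and no way to reverse it. What may have been a temporary gap becomes a permanent one. If the subject comes back to the same clinic, the motor score at the next visit, any adverse event and any lead revision fall outside the study. Section 19.4 ties reporting of serious adverse events, device effects and device deficiencies to the end of study participation, so closing the subject ends safety capture as well as effectiveness data. Section 18.8, in its risk-benefit rationale, calls for observation and follow-up of all patients.

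If those who drop out of contact differ in outcome from those who do not, the later means and event rates would be affected by informative dropout. That is plausible in a five-year Parkinson's disease study, but nothing in the documents demonstrates it.

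**Working it through.** The plan states no figure on this point, so there is none to reproduce. The check has three parts.

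**1. The two sections side by side**

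- Trigger (9.3): scheduled visits missed, contact attempts made, subject still unreachable. No time limit.
- Status (9.3): withdrawn, with loss to follow-up as the reason.
- Consequence (9.2): "Additional study data may no longer be collected after the point at which a subject has been withdrawn from the study". The bar covers subjects who have been withdrawn as well as those who withdraw consent.
- Return: neither 9.2 nor 9.3 provides for it, and the visible text of 9.4 adds only the definition of enrolment.

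**2. Can a subject be closed before the next visit is due?**

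Inputs are the visit times and windows in Sections 10.8 to 10.10, with a week as 7 days and a year as 365 days. The gap is the opening of the next window minus the close of the present one.

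| Visit missed | Window closes | Next window opens | Gap | Later visits barred |
|---|---|---|---|---|
| Week 12 | 84 + 7 = day 91 | 182 − 21 = day 161 | 70 days | 6 (Week 26, Years 1–5) |
| Week 26 | 182 + 21 = day 203 | 365 − 45 = day 320 | 117 days | 5 (Years 1–5) |
| Year 1 | 365 + 45 = day 410 | 730 − 45 = day 685 | 275 days | 4 (Years 2–5) |

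Three calls and a letter fit inside any of these gaps. The text therefore permits closure before the next window opens; it does not require it.

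**3. Illustration of size (assumed rates)**

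The visible text gives no sample size or dropout rate. Assume that a proportion p = 3% of subjects still in the study become unreachable at each annual visit, that all are declared lost, and that under a changed rule a fraction r of those lost before Year 5 would resume by the next visit. A subject unreachable at Year 5 has no later visit to return to, so r applies to the first four visits only.

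- Present rule: 1 − (1 − p)^5 = 1 − 0.97^5 = 14.1%.
- Resumption allowed: 1 − [1 − p(1 − r)]^4 × (1 − p).
- r = 1/3: p(1 − r) = 2%, so 1 − 0.98^4 × 0.97 = 10.5%.
- r = 1/2: p(1 − r) = 1.5%, so 1 − 0.985^4 × 0.97 = 8.7%.

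The reduction is 14.1 − 10.5 = 3.6 or 14.1 − 8.7 = 5.4 percentage points. For small p it is roughly 4pr, so it scales almost in proportion to both assumed inputs, and it is zero if nobody would return.

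**The case against.** A reader might infer that one missed visit removes a subject for the rest of the five years. The documents do not support that. Section 9.3 speaks of scheduled visits in the plural, asks for every effort to regain contact, and requires that the subject remain unreachable; Section 9.2 adds at least three documented attempts. A subject who misses a visit but is reached, or who returns before being declared lost, stays in the study. Nor does the text say that the status is assigned as soon as the attempts fail: with no deadline in either direction, a site may keep trying. These points stand and set the limits of the concern.

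Two further inferences also go too far. Long-term outcomes are not a visibly stated purpose: the objective in Section 6 refers to documenting patient outcomes including effectiveness, with safety parameters also collected, and the only endpoint and hypothesis shown are at 12 weeks. And nothing shows that subjects who lose contact and later return are doing worse, so a direction of bias cannot be claimed.

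It can also be said that a return or missed-visit rule may sit in text that is not visible (the data-collection table, Section 9.7, Section 11.2.3, further statistical detail), and that Section 14 already requires deviations to be recorded, which plausibly covers missed visits. The first cannot be excluded, but 9.2 and 9.3 read as complete and refer to no such rule. The second would document the gap without lifting the bar on data after it.

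**Conclusion.** The concern holds in a limited form. The protocol contains an explicit rule, not merely a missing detail, under which an implanted subject who has not revoked consent but has been declared lost can add no further study data on return. Data collected before that point are kept, and the intent-to-treat definition in Section 11.2.1 does not remove the subject.

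The Week 12 primary endpoint is little affected. The exposure is to effectiveness and safety data from Week 26 to Year 5: up to five scheduled visits for a subject declared lost after a missed Week 26 visit, four after a missed Year 1 visit. How many subjects this would involve cannot be estimated from the visible text. The figures of 14.1% against about 10.5% or 8.7% rest on an assumed 3% per year, on every unreachable subject being declared lost, and on assumed return fractions of one third and one half; they show scale only. This is a cheap improvement, not a flaw that threatens the main conclusion.

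**What to change.** In Section 9.3, replace the final paragraph so that:

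- a gap that remains after the documented contact attempts is recorded as a missed visit;
- the subject stays in the study and resumes the schedule if contact is regained;
- lost to follow-up is assigned, and the End of Study form completed, only if there has been no contact by the close of the Year 5 visit window.

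In Section 9.2, state that the bar on further data does not apply to subjects who were only out of contact and have not withdrawn consent.

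The cost is protocol wording and a missed-visit entry in the eCRF, with no new study procedure and no change to a subject's right to withdraw. Subject status stays open longer. Under Section 16.3 the amendment needs ethics committee review and approval before it takes effect and, if the consent form changes, a decision on whether participants must consent again.
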